10.4 Study Drug Administration

The cePolyTregs will be infused intravenously into an 18-gauge (or larger) intravenous catheter, either through a peripheral vein (preferred) or central vein. The cells are drawn into a 60 mL syringe via a plasma transfer set and manually infused. A leukoreduction filter must not be used for the infusion.

Emergency medical equipment (i.e., emergency crash cart) must be available during the infusion in case the subject has an allergic response, severe hypotensive crisis, or any other reaction to the infusion. Vital signs (temperature, respiration rate, pulse, SpO₂, and blood pressure) will be

taken before and for a minimum of 30 minutes after infusion and until these signs are satisfactory and stable.

10.5 Management of Infusion/Hypersensitivity Reactions

As noted above, emergency medical equipment (i.e., emergency crash cart) must be available during the infusion in case the subject has an allergic response, severe hypotensive crisis, or any other reaction to the infusion. Vital signs (temperature, respiration rate, pulse, SpO₂, and blood pressure) will be taken before and for a minimum of 30 minutes after infusion and until these signs are satisfactory and stable. Sites should be instructed to follow their institutional standard operating procedures for the management of infusion/hypersensitivity reactions, should they occur.

10.6 Prior and Concomitant Medications

Restrictions that apply to the period before the first admission are described in Section [9.2](#). Details of prior and concomitant medications and treatments will be collected at the time of enrollment and throughout the study.

All subjects in both parts of the study will receive standard of care treatment for COVID-19, including dexamethasone and other approved therapies for ARDS associated with SARS-CoV-2 infection per institutional guidelines. Concomitant use of any investigational treatments other than cePolyTregs for COVID-19 will not be permitted.

10.7 Enrollment or Randomization and Blinding

It is the investigator's responsibility to ensure that subjects are eligible to participate in the study prior to enrollment and continue to remain eligible throughout the study.

In Part 1 of the study, subjects will be enrolled and treated with open-label cePolyTregs sequentially in the order in which they are screened.

In Part 2 of the study, subjects will be assigned a subject identification number after the informed consent is signed using a centralized interactive web response system (IWRS) or other secure methodology. At randomization (Day 0), a centralized schema will be applied to randomize subjects in a 1:1 ratio to cePolyTregs or placebo. The system will stratify the randomized subjects by study site. All subjects and investigators will be blinded to treatment group throughout Part 2 of the study. Other study center staff will not be blinded because of differences in the product labels for active vs placebo product (see Section [10.2](#)). The investigator may request emergency unblinding for safety reasons; subjects unblinded for safety reasons should continue in the study for assessment of outcomes. Subjects who are randomized but do not receive study drug may be replaced.

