8.8.5 Subject Replacement

Subjects experiencing a product-related DLT will discontinue dosing and be asked to remain in the study and complete all study visits through the EOS visit; these subjects will not be replaced. If a subject terminates early for a reason other than a toxicity during the Treatment Period, the subject may be replaced at the discretion of the Sponsor.

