9.2 Exclusion Criteria (Parts 1 and 2)

Subjects will be ineligible for enrollment in the study if they meet any of the following criteria:

1. Any history or sign of significant chronic active or recurrent infection or screening laboratory evidence consistent with a significant chronic active or recurrent infection requiring treatment with antibiotics, antivirals or antifungals (other than SARS-CoV-2); ongoing antimicrobial treatments will not be exclusionary if, in the opinion of the investigator, no active infection is present (other than SARS-CoV-2)
2. Receiving extracorporeal membrane oxygenation therapy
3. Moribund patients not expected to survive 24 hours after enrollment based on clinical assessment
4. History of significant underlying pulmonary disease (requiring home oxygen), renal disease (requiring dialysis for chronic kidney disease), hepatic disease (Child-Pugh score ≥ 7), or known history of cirrhosis.
5. Known or suspected immunodeficiency disease
6. Positive serology for HBV, HCV, or HIV at Screening

UCSF	Clinical Study Protocol No. UCSF-cePolyTregs-01	Page 39 of 72
------	---	---------------

7. Abnormal CBC defined by:
 - a. Platelet count < 75,000/mm³
 - b. White blood cell count < 2500/mm³
 - c. Absolute neutrophil count < 500/mm³
8. History of bone marrow or stem cell transplantation
9. Received any type of live attenuated vaccine < 1 month prior to Screening or is planning to receive any such live attenuated vaccine over the course of the study
10. History of lung cancer or any other malignancy requiring active treatment, except adequately treated basal cell carcinoma or in situ carcinoma of the uterine cervix
11. Any female who is pregnant or breastfeeding, or any female who is planning to become pregnant during the study and follow-up period
12. Any condition that, in the investigator's opinion, may compromise study participation, present a safety risk to the subject, or may confound the interpretation of the study results
13. A QT duration corrected for heart rate by Fridericia's formula (QTcF) > 450 millisecond (msec) for males or > 470 msec for females, based on either single or averaged QTcF values of triplicate ECGs obtained over a 3-minute interval
14. Currently enrolled in another investigational device or drug study

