11.12 Removal of Subjects from the Study

At any time, the investigator can remove a subject from the study or discontinue study drug dosing, if deemed necessary for the subject's safety. The Sponsor also reserves the right to terminate the study at any time. The reason for early treatment discontinuation and early withdrawal from the study will be collected in the eCRFs. Subjects who discontinue treatment early should continue to attend all Follow-up study visits unless they have withdrawn consent for any further follow-up.

If a subject requests or decides to withdraw consent from the study, all efforts will be made to complete and report the observations as thoroughly as possible up to the subject's date of study withdrawal.

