Investigators should use their clinical judgment to determine whether a subject is to be withdrawn due to an AE. In the event the subject requests to withdraw from study-related treatment or the study due to an AE, the subject should be asked to return for all remaining study visits. In the event a subject is withdrawn from the study, an ET Visit should be completed. All subjects experiencing AEs, including clinically significant abnormal laboratory values, whether associated with the study drug, must be monitored until the condition (1) returns to normal, (2) returns to the subject's baseline, (3) the investigator determines the AE has reached a stable outcome and is no longer clinically significant, or (4) the subject is considered lost to follow-up.

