14.12 Protocol Violations/Deviations

This study should be conducted as specified in this protocol. In the event of a significant deviation from the protocol, the investigator or designee will contact the Sponsor or its designee at the earliest possible time to determine the disposition of the subject involved. If necessary, the Sponsor, Medical Monitor, and investigator will decide whether the subject may continue in the study. Such a decision will be documented by the investigator and Sponsor, as appropriate.

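### After the single infusion, subjects can be removed from the study for safety, an AE or a deviation, and no outcome follow-up is specified beyond one early-termination visit

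*Combined protocol and SAP*

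**What the plan says.** **Routes out of the study.**
- Section 11.12: "At any time, the investigator can remove a subject from the study or discontinue study drug dosing", where the subject's safety calls for it.
- Section 12: "Investigators should use their clinical judgment to determine whether a subject is to be withdrawn due to an AE".
- Section 14.12: after a significant deviation, the sponsor, Medical Monitor and investigator "will decide whether the subject may continue in the study", if such a decision is needed.

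**What follows.** Section 12: "In the event a subject is withdrawn from the study, an ET Visit should be completed". Section 8.1.5 places that visit within 7 days of termination. Section 12 ends capture of AEs at the ET visit for these subjects.

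**Text that keeps subjects in.**
- Section 8.8.5 (and 8.1.5): subjects with a product-related DLT are to "be asked to remain in the study and complete all study visits through the EOS visit".
- Section 11.12: those who stop treatment early keep attending follow-up visits unless they withdraw consent for it.
- Section 12: those who themselves ask to withdraw because of an AE are asked to return for the remaining visits.
- Section 10.7: those unblinded for safety stay in for outcome assessment.

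**Eligibility.** Section 10.7 also requires the investigator to "ensure that subjects are eligible to participate in the study prior to enrollment and continue to remain eligible throughout the study". The Schedule of Events (5.2) reviews eligibility only at Screening and pre-dose on Day 0, and Section 11.1 reconfirms it before study drug is given.

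**Analysis.** Section 13.1 specifies an ITT analysis of time to recovery. Subjects who do not recover, or who die, are censored at Day 29. Nothing is said about a subject removed earlier.

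**The concern.** In a single-dose trial, stopping treatment and leaving the study are different events, and the removal clauses do not keep them apart. A subject removed by the investigator or sponsor has had the full intervention and belongs in the ITT comparison. Yet the plan describes no way to learn whether that subject recovered by Day 28 or was alive at Day 29 or Day 84.

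Safety problems and AEs plausibly go with poor prognosis, so the missing outcomes would not be a random sample, and the losses could differ by arm. Three things are exposed: the primary endpoint, the mortality endpoints in Section 8.6.3, and the Section 8.6.6-level safeguard in Section 8.8.6, which halts the study when cumulative mortality among treated subjects exceeds 50%. A death after removal could go uncounted there.

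**Working it through.** **1. The plan's own power figure.** Inputs from Section 13.2: 67 of 252 recovered by Day 14; medians 31.4 and 16 days; 50 per arm; two-sided alpha 10%.
- Control rate: −ln(1 − 67/252)/14 = 0.0221 per day. Median ln 2/0.0221 = 31.4 days; 28-day recovery 1 − (1 − 67/252)² = 46.1%.
- Active: 28-day recovery 1 − exp(−28 ln 2/16) = 70.3% (stated 70.2%).
- Expected recoveries: 50 × (0.461 + 0.703) = 58.2. Rate ratio: 31.4/16 = 1.96.
- Schoenfeld power: Φ(½ × √58.2 × ln 1.9625 − 1.645) = Φ(0.93) = 82.3%.
- Log-rank simulation, 10,000 replicates: 82.1% in continuous time, 81.6% with daily assessment. A two-proportion calculation gives 79.7%.

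The stated 80% is reproduced to within about 2 points. These calculations include no loss to follow-up.

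**2. Weight of one removed subject.** 1/50 = 2 points of an arm's recovery or mortality. If 3 to 5 subjects in one arm were removed (an assumption; the documents give no number), their unknown outcomes would span 6 to 10 points. The planned recovery difference is 70.2 − 46.1 = 24.1 points. This is a worst-case span, not an expected bias.

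**3. Sensitivity of the primary test.** Removal rates of 5, 10 and 20% are assumptions, as is removal time uniform over Days 0 to 14. The simulated test is an unstratified log-rank test. Because Section 13.1 does not say how a removed subject is censored, both readings were run.

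| Scenario | Censored at removal (5/10/20%) | Censored at Day 29 (5/10/20%) |
|---|---|---|
| Planned effect, removal unrelated to outcome, both arms: power | 80.4 / 80.3 / 77.5% | 79.4 / 78.3 / 72.2% |
| No effect, only active-arm non-recoverers removed: two-sided type I error | 11.2 / 13.1 / 20.5% | 9.7 / 10.6 / 10.1% |
| Same: false-benefit tail (nominal 5%) | 7.7 / 10.7 / 19.6% | 4.6 / 5.2 / 5.2% |

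The harm depends on who is removed and on a censoring rule that is not stated. Mortality at Days 29 and 84 has no comparable default: the outcome is simply unknown.

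**4. The clauses side by side.** A DLT is a related AE of grade 3 or higher (Section 8.8.3). Sections 8.1.5 and 8.8.5 ask that subject to stay through EOS. Section 12 lets the investigator withdraw a subject for any AE, which includes the same event. Section 12 also treats two similar subjects differently: one who asks to leave because of an AE is invited to all remaining visits, while for one withdrawn from the study only the ET visit is mentioned.

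**5. The eligibility sentence.** Inclusion criterion 1 requires under 72 hours of ventilation at enrollment, and criterion 2 requires PEEP above 5. Neither can hold through Day 84 in a subject who recovers. The Schedule of Events and Section 11.1 confine the check to the time before dosing.

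**The case against.** Several stronger readings are tempting, and the documents do not support them.

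- **Lost eligibility forces removal.** A reader might infer that recovery, a low platelet count, a long QTcF or "Receiving extracorporeal membrane oxygenation therapy" (an exclusion in Section 9.2) would put a subject out under Section 10.7. That section attaches no action to lost eligibility. The exclusions govern enrollment. ECMO falls in WHO category 7 (Section 11.6), and new treated respiratory infections are AESIs (Section 12.2), so the plan expects to observe such subjects.
- **Nothing remains to be stopped after infusion.** Not so. Aspirates, mini BAL and blood draws continue (5.2), ventilation and weaning follow protocol rules (11.13, Appendices A and B), and other investigational COVID-19 treatments are barred (10.6). Taking a subject off these for safety has a real purpose, and any fix must allow it.
- **The DLT text flatly contradicts the removal powers.** It is a default set against a discretionary power. The two are unreconciled, which is a weaker fault.
- **Removed subjects count as non-recovered to Day 29.** Section 13.1 does not say so.
- **All outcome information stops.** Sections 10.7, 11.12 and 12 keep several groups in follow-up. Section 12 requires existing AEs to be monitored to a stable outcome, and Section 12.6.2 provides for SAE follow-up to a definitive outcome, so some later deaths may be known.

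It is also fair that investigators are blinded in Part 2, that inflated type I error needs one-sided removal of non-recoverers together with censoring at removal, and that few subjects may ever be removed. What remains is a specific gap: no WHO category or vital status is required for a subject whom the investigator or sponsor takes out of the study. A censoring rule added in the SAP would not recover data that were never collected.

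**Conclusion.** The point holds in this limited form. Sections 11.12, 12 and 14.12 permit removal from the study for reasons plausibly tied to prognosis, and the only stated follow-up is an ET visit within 7 days. These clauses are not reconciled with the plan's own retention text. The eligibility sentence in Section 10.7 is a separate wording fault with no stated consequence.

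The size cannot be fixed from the documents. Each removed subject is 2 points of an arm. Under the assumed rates, 5 to 10% removal unrelated to outcome lowers power only to between 78% and 80%. Outcome-related removal in the active arm could roughly double the false-benefit tail at 10% removal, but only if subjects are censored at removal. Bias is possible here, not demonstrated. Because the repair is cheap, it should be made.

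**What to change.** - **10.7:** limit the eligibility requirement to the period up to study drug administration, in line with 11.1 and the Schedule of Events.
- **11.12, 12 and 14.12:** separate stopping study drug or study procedures, which the investigator may still do for safety, from ending outcome follow-up. State that after randomization in Part 2 (after infusion in Part 1) only withdrawal of consent for further follow-up ends outcome collection.
- **Subjects who stop visits or procedures without refusing record access:** obtain WHO category to Day 28 and vital status to Day 84 from records or by telephone. Deaths found this way should also reach the mortality count in 8.8.6.
- **12 and 11.12 against 8.1.5 and 8.8.5:** reconcile the text, so that one follow-up rule covers DLTs and other AEs.
- **13.1:** state how a subject whose follow-up is still incomplete is censored, with a sensitivity analysis.

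The cost is amended wording and a few record checks or calls. The investigator's clinical discretion over study drug and procedures is left as it is.

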10.8 Storage and Accountability

cePolyTregs will be kept in a monitored freezer in vapor phase LN2 until time of infusion. Stability after thawing is 4 hours. The long-term stability of cePolyTregs in LN2 freezers is provided in the current Investigator's Brochure.

The Sponsor or designee will supply the study drug. The site will maintain the following records: receipt of shipments, administration to subjects, and return of partially used, or unused study drug. Upon completion or early termination of the study, all unused and partially used investigational product must be returned to the Sponsor (or designated agent), unless the Sponsor authorizes the study site to destroy the investigational product.

11 STUDY PROCEDURES

The following assessments will be conducted during screening and at the time points specified in the Schedule of Events (SOE) (Section [5.2](#)). All missed visits must be documented in the subject's medical record and the appropriate eCRF.

11.1 Screening and Informed Consent

Each subject must sign and date the ICF before participating in any study-specific activities. The ICF may be signed prior to the Screening Visit.

After the ICF is signed, subjects in Part 2 will be assigned a unique subject identification number by IWRS or other secure methodology.

The subject number, assigned at the time of screening, will be used to identify the subject during the study and must be used on all study documentation related to that subject. The subject identification number will remain constant throughout the entire study and must not be changed after initial assignment. Each study site will maintain a list identifying all subjects by subject identification number and subject initials.

After completing the Screening Period, the subject will be evaluated by the investigator to confirm eligibility. A subject is considered to have started screening on the date that the Screening Visit is recorded. Screen failure subjects will be entered into the study records. Investigators will maintain a screening log of all potential study subjects that includes limited information about each candidate, including dates of screening and procedures, and the outcome of the screening process (e.g., enrolled into the study, reason for ineligibility, or withdrawal of consent).

At Baseline and before any study drug is administered, potential subjects will be reviewed by the site to reconfirm their eligibility.

11.2 Demographics and Medical/Surgical History

Demographic data will be collected, including each subject's sex, age, race, and ethnicity. Where local regulations do not permit certain demographic data to be collected, collection of those data will not be required.

The investigator or designee will collect the subject's medical and surgical histories. All findings will be recorded on the medical history and surgical history eCRFs.

11.3 Physical Examination

The investigator or designee will conduct a complete physical examination as outlined in the SOE. Physical examination clinically significant findings prior to the first dose of study drug administration will be recorded on the medical history eCRF; clinically significant, treatment-emergent findings after the first study drug dose will be recorded as AEs.

At a minimum, the *complete physical examination* (Baseline) should include assessments of the skin, head and neck, lungs, cardiovascular system, abdomen, and extremities. A *targeted physical examination* (all other visits) will include assessment of any new subject complaints or changes from baseline.

11.4 Vital Signs

The following vital sign measurements will be performed: systolic and diastolic blood pressure, pulse, respiration rate, SpO₂, and temperature (height and weight at the Screening Visit only). Vital signs (except for temperature and weight) will be monitored periodically for a minimum of 30 minutes after administration of IP. Subject must be seated or in a semi-recumbent position in a rested, calm state for at least 3 minutes before vital signs are collected.

11.5 12-Lead Electrocardiography

12-Lead ECGs will be obtained locally on standard ECG equipment available at the study site. The subject must be in a semi-recumbent or supine position in a rested, calm state for at least 10 minutes before ECG assessment is performed. Each 12-lead ECG should be performed prior to blood draws, dosing, or other invasive procedures whenever possible.

The investigator or designated study site physician will review, sign, and date all ECGs.

Any clinically significant, treatment-emergent abnormal ECG findings will be recorded as an AE.

11.6 WHO Severity Scale for COVID-19 Pulmonary Syndrome

The WHO ordinal severity scale ([Figure 2](#)) was derived by a special WHO committee to measure illness severity over time ([World Health Organization 2020](#)). Subject status will be assessed using the severity scale at the intervals described in the SOE.

Figure 2. WHO Ordinal Scale for COVID-19 Clinical Improvement

Patient State	Descriptor	Score
Uninfected	No clinical or virological evidence of infection	0
Ambulatory	No limitation of activities	1
	Limitation of activities	2
Hospitalized Mild disease	Hospitalized, no oxygen therapy	3
	Oxygen by mask or nasal prongs	4
Hospitalized Severe Disease	Non-invasive ventilation or high-flow oxygen	5
	Intubation and mechanical ventilation	6
	Ventilation + additional organ support – pressors, RRT, ECMO	7
Dead	Death	8

11.7 Sequential Organ Failure Score (SOFA)

The SOFA score is an objective score that allows for calculation of both the number and severity of organ dysfunction in 6 organ systems (respiratory, coagulation, liver, cardiovascular, renal, and neurologic; [Jones 2009](#)) ([Table 2](#)). The score can measure individual or aggregate organ dysfunction. The SOFA will be assessed at the intervals specified in the SOE.

Table 2. The Sequential Organ Failure Assessment (SOFA) Score

SOFA score	1	2	3	4
Respiration ^a				
PaO ₂ /FIO ₂ (mm Hg)	<400	<300	<220	<100
SaO ₂ /FIO ₂	221-301	142-220	67-141	<67
Coagulation				
Platelets ×10 ³ /mm ³	<150	<100	<50	<20
Liver				
Bilirubin (mg/dL)	1.2-1.9	2.0-5.9	6.0-11.9	>12.0
Cardiovascular ^b				
Hypotension	MAP <70	Dopamine ≤5 or dobutamine (any)	Dopamine >5 or norepinephrine ≤0.1	Dopamine >15 or norepinephrine >0.1
CNS				
Glasgow Coma Score	13-14	10-12	6-9	<6
Renal				
Creatinine (mg/dL) or urine output (mL/d)	1.2-1.9	2.0-3.4	3.5-4.9 or <500	>5.0 or <200

CNS = central nervous system; MAP = mean arterial pressure; SaO₂ = peripheral arterial oxygen saturation.

^a PaO₂/FIO₂ ratio was used preferentially. If not available, the SaO₂/FIO₂ ratio was used.

^b Vasoactive medications administered for at least 1 hr (dopamine and norepinephrine µg/kg/min).

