8.6.3 Secondary Efficacy Endpoints

Part 2 (Phase 2a):

Efficacy of cePolyTregs compared with placebo/SOC, as assessed by:

- The proportion of subjects with a 2-point or greater improvement in the WHO severity scale for COVID-19 pulmonary syndrome on each of Study Days 7, 14, 21, and 28
- The proportion of subjects with improvement in the WHO severity scale for COVID-19 pulmonary syndrome to Grade 3 or less on each of Study Days 7, 14, 21, and 28
- The proportion of subjects requiring mechanical ventilation on each of Study Days 7, 14, 21 and 28
- Number of days free of mechanical ventilation on Days 29 and 57
- Mean and median Sequential Organ Failure [SOFA] scores on each of Study Days 7, 14, 21 and 28
- Change in chest imaging (radiograph or CT scan) abnormalities
- All-cause mortality on Study Days 29 and 84

Parts 1 and 2:

Pharmacodynamic and biomarker changes associated with administration of cePolyTregs compared with placebo/SOC, including but not limited to:

- Change from baseline in circulating cePolyTregs
- Change from baseline in pulmonary cePolyTregs by endotracheal aspirate and mini BAL

UCSF	Clinical Study Protocol No. UCSF-cePolyTregs-01	Page 35 of 72
------	---	---------------

- Change from baseline in ferritin, C-reactive protein, LDH, and high-sensitivity troponin I (hs-TnI)
- Change from baseline in d-dimer
- Change from baseline in absolute lymphocyte count
- Change from baseline in C3, C4, and CH50
- Change from baseline in inflammatory cytokines/chemokines, e.g. IL-6, IL-12, IFN γ , TNF α , MCP-1 and MCP-4
- Phenotypic and functional changes from baseline in immune subsets using cytometric, genomic and/or proteomic analyses of cells harvested from endotracheal tubes, mini BAL, and blood

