11.8 Mechanical Ventilation Status

If the patient is receiving invasive mechanical ventilation, ventilatory parameters will be collected daily between 06:00 and 10:00, including the following, per local procedure:

Mode of ventilation, FiO₂(Fraction of inspired oxygen), SpO₂ , plateau pressure, peak pressure, PEEP (Positive End-Expiratory Pressure). If an ABG (arterial blood gas) is obtained during that time, then the PaO₂ (Partial pressure of arterial oxygen) will also be collected.

If the patient is receiving non-invasive ventilation, the level of inspiratory pressure, FIO₂, and PEEP will be registered. If the patient is receiving high-flow oxygen, the flow rate and the FIO₂ will be recorded.

The proportion of subjects requiring mechanical ventilation will be assessed on Study Days 7, 14, 21, and 28, and the number of days free of mechanical ventilation will be assessed on Days 28 and 56.

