APPENDIX B Ventilator Weaning Procedure

Commencement of Weaning (applicable to subjects ventilated invasively or non-invasively)

Subjects will be assessed for the following weaning readiness criteria each day between 0600 and 1000 hours. If a subject's procedure, test, or other extenuating circumstance prevents assessment for these criteria between 0600 and 1000, then the assessment and initiation of subsequent weaning procedures may be delayed for up to 6 hours.

1. At least 12 hours since enrollment in the trial
2. $\text{FiO}_2 \leq 0.40$ and $\text{PEEP} \leq 8 \text{ cm H}_2\text{O}$ or $\text{FiO}_2 \leq 0.50$ and $\text{PEEP} = 5 \text{ cm H}_2\text{O}$
3. Values of both PEEP and $\text{FiO}_2 \leq$ values from previous day
4. Not receiving neuromuscular blocking agents and without neuromuscular blockade
5. Subject exhibiting inspiratory efforts. If no efforts are evident at baseline, ventilator set rate will be decreased to 50% of baseline level for up to 5 minutes to detect inspiratory efforts.
6. Systolic arterial pressure $\geq 90 \text{ mm Hg}$ without vasopressor support ($\leq 5 \mu\text{g/kg/min}$ dopamine or dobutamine will not be considered a vasopressor)

Spontaneous Breathing Trial Procedure and Assessment for Unassisted Breathing

If criteria 1 to 6 above are met, then initiate a trial of up to 120 minutes of spontaneous breathing with $\text{FiO}_2 < 0.5$ using any of the following approaches:

1. Pressure support (PS) $< 5 \text{ cm H}_2\text{O}$, $\text{PEEP} < 5 \text{ cm H}_2\text{O}$
2. CPAP $< 5 \text{ cm H}_2\text{O}$
3. T-piece
4. Tracheostomy mask

The clinical team may decide to change mode during spontaneous breathing (PS = 5, CPAP, tracheostomy mask, or T-piece) at any time during the spontaneous breathing trial.

Monitor for tolerance using the following:

1. $\text{SpO}_2 \geq 90\%$ and / or $\text{PaO}_2 \geq 60 \text{ mm Hg}$
2. Mean spontaneous tidal volume $\geq 4 \text{ ml/kg PBW}$ (if measured)
3. Respiratory Rate $\leq 35 / \text{min}$
4. $\text{pH} \geq 7.30$ (if measured)
5. No respiratory distress (defined as 2 or more of the following):
 - a. Heart rate $\geq 120\%$ of the 0600 rate ($\leq 5 \text{ min}$ at $> 120\%$ may be tolerated)
 - b. Marked use of accessory muscles

- c. Abdominal paradox
- d. Diaphoresis
- e. Marked subjective dyspnea

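### The SOFA respiratory score changes scale when no blood gas is available, which can lower SOFA by 1 to 2 points at SpO2 of about 88-96% partly independently of lung improvement

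*Combined protocol and SAP*

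**What the plan says.** Section 11.7, Table 2, gives two rows for the respiratory component. For 1, 2, 3 and 4 points the PaO2/FiO2 cut-offs are "<400 <300 <220 <100" and the SaO2/FiO2 bands are "221-301 142-220 67-141 <67". Footnote a makes PaO2/FiO2 the preferred ratio: it "ratio was used preferentially. If not available, the" SaO2/FiO2 ratio takes over. The table notes define SaO2 as "peripheral arterial oxygen saturation", so the fallback needs no blood gas.

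Neither the Schedule of Events nor Table 3 (clinical laboratory parameters) schedules a blood gas. Section 11.8 lists the ventilator data collected daily between 06:00 and 10:00 under invasive ventilation and adds PaO2 only conditionally: "If an ABG (arterial blood gas) is obtained during that time". For non-invasive ventilation it lists inspiratory pressure, FiO2 and PEEP. For the next step down it says "If the patient is receiving high-flow oxygen, the flow rate and the" FiO2 are recorded. It states nothing for mask or nasal prongs, which is WHO category 4 in section 11.6.

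Section 8.6.3 makes this a Part 2 secondary efficacy endpoint: "Mean and median Sequential Organ Failure [SOFA] scores on each of Study Days 7, 14, 21 and 28". Section 13.8 compares continuous variables between arms by t-test or Wilcoxon test. No rule covers a change of ratio within a subject or between subjects.

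**The concern.** A two-ratio rule is harmless if both rows give the same patient the same score, or if the choice of row is unrelated to clinical course. Neither is assured here. As the documents describe data collection, PaO2 is available mainly while a subject is invasively ventilated, so extubation tends to move a subject from one row to the other. If the second row is more lenient, part of a fall in SOFA over time reflects the change of scale. If the arms are extubated at different rates, part of a between-arm SOFA difference does too.

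**Working it through.** The documents give no figure for how far the rows differ, so there is none to reproduce. The check scores the same physiological state on both rows.

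**1. A pair of values from the protocol.** Appendix B uses SpO2 90% and PaO2 60 mm Hg as tolerance limits for the breathing trial. They serve here as a worked example only. P/F = 60/FiO2 and S/F = 90/FiO2, with S/F rounded to a whole number because the bands are integers.

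| FiO2 | P/F | points | S/F | points | gap |
|---|---|---|---|---|---|
| 0.30 | 200 | 3 | 300 | 1 | 2 |
| 0.40 | 150 | 3 | 225 | 1 | 2 |
| 0.50 | 120 | 3 | 180 | 2 | 1 |
| 0.80 | 75 | 4 | 112 | 3 | 1 |
| 1.00 | 60 | 4 | 90 | 3 | 1 |

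Over FiO2 0.30 to 1.00 in steps of 0.01, the gap is 1 point at 57 of 71 values and 2 points at 14. Appendix B's weaning readiness limits are FiO2 0.40 or 0.50 depending on PEEP, where the gap is 2 and 1.

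**2. Where the rows would agree.** The cut-offs line up when PaO2 divided by saturation in percent equals 400/301 = 1.33, 300/220.5 = 1.36, 220/141.5 = 1.55 or 100/67 = 1.49. At SpO2 88-95% that means PaO2 from 88 × 1.33 = 117 to 95 × 1.55 = about 148 mm Hg.

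**3. Other saturations (assumption).** The documents give no PaO2-to-saturation relation. I assumed the Severinghaus curve, S = 100/(23400/(P³ + 150P) + 1). Counts are over the same 71 FiO2 values.

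| PaO2 | SpO2 % | reversed by 1 | gap 0 | gap 1 | gap 2 | gap 3 |
|---|---|---|---|---|---|---|
| 55 | 88.2 | 0 | 0 | 53 | 18 | 0 |
| 65 | 92.4 | 0 | 0 | 59 | 11 | 1 |
| 75 | 94.9 | 0 | 8 | 52 | 11 | 0 |
| 80 | 95.7 | 0 | 13 | 49 | 9 | 0 |
| 90 | 96.9 | 0 | 22 | 44 | 5 | 0 |
| 100 | 97.7 | 0 | 33 | 38 | 0 | 0 |
| 120 | 98.7 | 0 | 50 | 21 | 0 | 0 |
| 150 | 99.3 | 10 | 59 | 2 | 0 | 0 |

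Across SpO2 88-95% with P/F below 300, the gap is 0 in 3.1% of grid cells, 1 in 77.5%, 2 in 19.0% and 3 in 0.4%. Across PaO2 50-150 with P/F below 300 and no saturation limit, it is 0 in 40.9%, 1 in 51.2%, 2 in 7.9% and 3 in 0.1%. On room air at SpO2 96.9%, P/F = 90/0.21 = 429 and S/F = 96.9/0.21 = 461. Both score 0, so there is no gap. The grids weight cells equally and are not patient frequencies.

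**4. Effect on the comparison.** Artefact = mean gap × difference between arms in the proportion scored on the fallback. As a ceiling, suppose recovery ends all gas sampling, every unrecovered subject has a gas, and the arms recover as section 13.2 plans:

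- Day 14: 0.455 − 0.266 = 0.189; × 2 points = 0.38.
- Day 28: 0.702 − 0.461 = 0.241; × 2 points = 0.48.

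Recovered subjects on room air at about 97% or above have a gap of 0, so the lower bound is 0.

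**The case against.** Several points on the other side stand.

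- **Cause.** A reader might infer that SOFA falls because gases stop and not because lungs improve. The documents do not support that. They give no blood-gas frequencies, extubation itself usually reflects better lungs, and only one of six SOFA components is affected.
- **Universality.** A reader might take 1 to 2 points as a general offset. It is not one: the gap is mostly 0 near 99% saturation and can reverse.
- **Inference.** If treatment does not affect ventilation, randomisation balances gas availability and both means shift alike. The switch can exaggerate a real respiratory benefit; it would not produce one from nothing.
- **The ceiling.** Recovery (WHO 0-4) is not the same as extubation, since WHO 5 is already extubated. The section 13.2 rates take no account of death.
- **Source of PaO2.** The morning window in section 11.8 governs ventilator parameters. Nothing says SOFA may use only that PaO2, although no other collection after enrolment is specified.
- **Appendix B.** The two limits are joined by an and/or. They are not declared equivalent.
- **SAP.** Section 13 defers detail to a separate SAP, where a scoring rule could still be set.

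None of this removes the switch, the misaligned rows at 88-96%, or the lack of any rule for handling them.

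**Conclusion.** The concern holds in a limited form. Footnote a lets the respiratory scale change with blood-gas availability, and at SpO2 of about 88-96% the fallback row usually scores the same patient 1 to 2 points lower. The worked case of 3 versus 1 rests on the protocol's own numbers; the spread across saturations rests on the assumed dissociation curve. Losing the gas can therefore lower SOFA partly independently of lung improvement. How much of any observed fall this explains cannot be derived from the documents.

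The possible exaggeration of a between-arm difference runs from 0 to about 0.4 points at Day 14 and 0.5 at Day 28. The upper values need an average gap of 2 points, the planned recovery rates and complete separation of gas sampling by recovery status. This matters for interpreting a secondary endpoint. The primary endpoint, time to recovery on the WHO scale, is unaffected.

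**What to change.** - Record on the eCRF which ratio was used at each SOFA assessment.
- In the SAP, prespecify a second SOFA analysis that scores respiration from SpO2/FiO2 for every subject and visit. Report it beside the footnote a version, and claim a SOFA difference only if the two agree. SpO2 is already part of the vital signs. This keeps the measured PaO2 in use while showing whether the result depends on the change of scale.
- In section 11.8, also record FiO2 or oxygen flow for mask or nasal prongs, with one fixed flow-to-FiO2 conversion. Without it, neither ratio has a stated denominator in WHO category 4.

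The cost is SAP and footnote wording plus one or two eCRF fields. The downside is that SpO2/FiO2 discriminates poorly near 100% saturation, which is why it should sit beside the existing score and not replace it.
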